WOCBP	Women of Child Bearing Potential
ANC	Absolute Neutrophil Count
ULN	Upper Limit of Normal
GFR	Glomerular Filtration Rate
CBC	Complete Blood Count
CMP	Comprehensive Metabolic Panel
DLT	Doses Limiting Toxicity
PR	Partial Response
CR	Clinical Response
SD	Stable Disease

1 PROTOCOL SUMMARY

1.1 SYNOPSIS

Protocol Title: A Phase II study of induction SBRT and olaparib followed by combination pembrolizumab/olaparib in gastric and gastroesophageal junction (GEJ) cancers

Objectives:

Primary Objective:

- To assess the anti-tumor efficacy of combined therapy as determined by measurement of objective response rate (ORR)

Secondary Objectives:

- To assess the anti-tumor efficacy of combined therapy as determined by measurement of overall survival (OS), progression free survival (PFS), duration of response (DOR) and disease control rate (DCR) as a total cohort and HRD (Homologous Recombination Deficiency) versus HR (Homologous Recombination) proficient.
- To evaluate the safety and tolerability of radiotherapy added to olaparib.

Tertiary/ Exploratory Objective:

- To define the effect of HRD on combination SBRT (Stereotactic Beam Radiation Therapy), olaparib, and pembrolizumab on immunomodulation as measured by immune cell infiltration and activation in plasma/serum assays and tissue.

Endpoint:

Primary Endpoint:

- Objective Response Rate of unirradiated tumors (ORR per RECIST 1.1)

Secondary Endpoints:

- Overall Survival (OS) from the initiation of therapy to the date of death or to the date of last follow-up.
- Progression Free Survival (PFS) from the initiation of therapy to the date of progression or to the date of last follow-up.
- Duration of response (DoR) defined as the time from documentation of tumor response to disease progression.

- Disease control rate (DCR) defined as the sum of partial response (PR), complete response (CR) and stable disease (SD).
- Treatment-emergent adverse events (AEs), serious adverse events (SAEs) of combination SBRT and olaparib

Tertiary/ exploratory:

- Immune changes in tumor tissue and plasma at baseline compared to after combination SBRT/olaparaib and after Olaparib/pembrolizumab
- Assess response based on HRD status, PD-L1 expression, MMR (Mismatch Repair)/MSI (Microsatellite Instability), and TMB (Tumor Mutational Burden) in tumor
- Changes in cytokines, ctDNA in plasma/serum
- Abscopal effect based on irradiated disease site

Population:

Sample size

- *Maximum number of participants that can be enrolled is 32 (allow for screen failures)*
- *Minimum number of participants to be enrolled 26 (between two cohorts: 13 in the HR deficient cohort, 13 in the HR proficient cohort) (number of participants needed to answer scientific question/aims)*

Phase:

II

Participating Sites:

University of Colorado Hospital (UCHealth Metro and Highlands Ranch Hospital)
 Memorial Hospital (UCHealth South)

Description of Study Intervention:

Concurrent SBRT with Olaparib followed by combination Olaparib and Pembrolizumab

[figure not shown]
Study Duration:

Enrollment will last approximately 3 years. Total length of study is 4 years. Enrollment is anticipated at 8 per year

Participant Duration:

1 year from study initiation

1.2 STUDY SCHEMA

1.3 SCHEDULE OF EVENTS

Trial Period:	Screening Phase	Treatment Cycles ^a					End of Treatment	Post-Treatment	
Treatment Cycle/Title:	Study Screening	Day 1 Cycle 1 ^a	Day 8 Cycle 1	Day 15 Cycle 1	Day 1 Cycle>1 ^e	Every 9 weeks	Discontinue ^b	30 Day Safety Follow Up ^k	Follow Up
Scheduling Window (Days):	-28 to -1		+/- 1	+/- 1	± 7	± 3	At time of Discontinuation (+/- 7)	+7	Q12W (+/- 7)
Administrative Procedures									
Informed Consent	x								
Inclusion/Exclusion Criteria	x								
Demographics and Medical History ^j	x								
Prior and Concomitant Medication Review	x	x	x	x	x		x	x	
Radiation ^p		x							
Olaparib ^o		x	x	x	x				
Pembrolizumab					x				
Clinical Procedures/Assessments									
Review Adverse Events		x	x	x	x		x	x	
Full Physical Examination	x								
Directed Physical Examination		x	x	x	x		x	x	
Vital Signs and Weight ^f	x	x	x	x	x		x	x	
ECOG Performance Status ⁱ	x	x	x	x	x		x	x	
Survival Status								x	x
Laboratory Procedures/Assessments: analysis performed by LOCAL laboratory^m									
Pregnancy Test – Urine or Serum β-HCG ^c	x	x			x				
PT/INR and aPTT	x	x			x		x		
CBC with Differential	x	x	x	x	x		x		
Comprehensive Serum Chemistry Panel	x	x	x	x	x		x		
Urinalysis	x	x			x		x		
Total T3, FT4 and TSH	x				x ^g		x		
ECG ^l	x								
Efficacy Measurements									
Tumor Imaging ^h	x					x	x ^s		x ⁿ

Trial Period:	Screening Phase	Treatment Cycles ^a					End of Treatment	Post-Treatment	
Treatment Cycle/Title:	Study Screening	Day 1 Cycle 1 ^a	Day 8 Cycle 1	Day 15 Cycle 1	Day 1 Cycle>1 ^e	Every 9 weeks	Discontinue ^b	30 Day Safety Follow Up ^k	Follow Up
Scheduling Window (Days):	-28 to -1		+/- 1	+/- 1	± 3	± 3	At time of Discontinuation (+/- 7)	+7	Q12W (+/- 7)
Tumor Biopsies/Archival Tissue Collection/Correlative Studies Blood									
Biopsy Tissue Collection ^d	x				x				
Correlative studies blood collection ^d	x				x		x		

^a For Cycle 1 only, patient will be seen weekly. All other cycles as listed in schedule of events

^b All patients with clinically significant abnormal laboratory results at treatment completion or study drug discontinuation (EOT) visit are to be followed until the results return to normal (or patient's baseline), or until a valid reason, other than a drug- related effect, is identified. Patients with an unresolved AE or SAE event at treatment completion or study drug discontinuation will be contacted by the investigator or his or her designee to determine the status of the event until the event is resolved or stabilized, the patient is lost to follow up, or it has been determined that the study treatment or participation is not the cause of the event. If the post-trial visit occurs less than 30 days after the last dose of study treatment, a subsequent follow-up phone call should be made at 30 days post the last dose of study treatment to determine if any adverse events have occurred since the post-trial clinic visit

^c Pregnancy test on blood or urine samples will be performed for pre-menopausal women of childbearing potential one within 28 days prior to the start of study treatment and the other on Day 1 of the study prior to commencing treatment. Tests will be performed by the hospital's local laboratory. If results are positive the patient is ineligible/must be discontinued from the study. In the event of a suspected pregnancy during the study, the test should be repeated.

^d First biopsy and correlative bloodwork to be collected prior to C1D1 (within 14 days of starting therapy). For baseline biopsy only, available archived tumor tissue of a metastatic tumor collected up to 28 days prior to registration is acceptable. Second biopsy and correlative bloodwork to be collected within 5 days prior to C2D1, before treatment with olaparib/pembrolizumab. Third biopsy and correlative bloodwork to be collected within 5 days prior to C4D1, before starting treatment with olaparib/pembrolizumab. Correlative bloodwork only within 5 days of EOT.

^e Cycle 2 Day 1 should start within two weeks of completing combination olaparib and radiation.

^f Vital signs should include temperature, pulse, respiratory rate, weight and blood pressure. Height will be measured at screening only.

^g Perform on Day 1 of every cycle starting from Cycle 2 and at EOT

^h Tumor imaging is strongly preferred to be acquired by computed tomography (CT). For the abdomen and pelvis, contrast-enhanced magnetic resonance imaging (MRI) may be used when CT with iodinated contrast is contraindicated, or when local practice mandates it. MRI is the strongly preferred modality for imaging the brain. The same imaging technique regarding modality, ideally the same scanner, and the use of contrast should be used in a participant throughout the study to optimize the reproducibility of the assessment of existing and new tumor burden and improve the accuracy of the assessment of response or progression based on imaging.

ⁱ Evaluation of ECOG at screening is to be performed within 14 days prior to the date of treatment.

^j Medical history will include all active conditions and any condition diagnosed within the prior 10 years that are considered to be clinically significant by the Investigator

^k The investigator or qualified designee will review all new anti-neoplastic therapy initiated after the last dose of trial treatment. If a participant initiates a new anti-cancer therapy within 30 days after the last dose of trial treatment, the 30 day Safety Follow-up visit must occur before the first dose of the new therapy. Once new anti-cancer therapy has been initiated the participant will move into survival follow-up. If the post-trial visit occurs less than 30 days after the last dose of study treatment, a subsequent follow-up phone call should be made at 30 days post the last dose of study treatment to determine if any adverse events have occurred since the post-trial clinic visit

^l ECGs are required within 7 days prior to starting study treatment

^m Laboratory tests for screening or entry into the Second Course Phase should be performed within 10 days prior to the first dose of treatment. After Cycle 1, pre-dose laboratory procedures can be conducted up to 72 hours prior to dosing. Results must be reviewed by the investigator or qualified designee and found to be acceptable prior to each dose of trial treatment.

ⁿ In participants who discontinue study treatment without documented disease progression, every effort should be made to continue monitoring their disease status by tumor imaging using the same imaging schedule used while on study treatment (every 12 weeks \pm 7 days) until the start of a new anticancer treatment, disease progression, pregnancy, death, withdrawal of consent, or the end of the study, whichever occurs first.

^o Drug diaries will be collected and reviewed at the end of each cycle for Olaparib compliance. Additionally, patients should bring any bottles dispensed for the previous cycle with them to each clinic visit (starting at Day 1 cycle 2) for compliance.

^p The simulation planning scan needs to be completed prior to treatment start date. A radiation oncology assessment will occur at least once during the SBRT course as per standard of care. At 2 weeks post-SBRT, a radiation oncology nurse will call patient to assess for any further toxicities. See section 4.3 for additional radiation details.

^q Only Concomitant Medications related to the treatment of AE or SAE, and other medical conditions deemed necessary by the PI will be recorded.

^r For patients who come off treatment for reasons other than progression, follow up scans will be recorded every 12 weeks. Participants who experience confirmed disease progression or start a new anticancer therapy, will move into the Survival Follow-Up Phase and should be contacted by telephone every 12 weeks to assess for survival status until death, withdrawal of consent, or the end of the trial, whichever occurs first. Patients will be followed for 5 years for survival

^s EOT scans are only required if a scan has not been performed within 8 weeks prior to the EOT visit

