2.4 OLAPARIB BACKGROUND

Olaparib (AZD2281, KU-0059436) is a potent Polyadenosine 5'diphosphoribose [poly (ADP ribose)] polymerisation (PARP) inhibitor (PARP-1, -2 and -3) that is being developed as an oral therapy, both as a monotherapy (including maintenance) and for combination with chemotherapy and other anti-cancer agents. PARP inhibition is a novel approach to targeting tumors with deficiencies in DNA repair mechanisms. PARP enzymes are essential for repairing DNA single strand breaks (SSBs). Inhibiting PARPs leads to the persistence of SSBs, which are then converted to the more serious DNA double strand breaks (DSBs) during the process of DNA replication. During the process of cell division, DSBs can be efficiently repaired in normal cells by homologous recombination repair. Tumors with HR deficiencies (HRD), such as ovarian cancers in patients with BRCA1/2 mutations, cannot accurately repair the DNA damage, which may become lethal to cells as it accumulates. In such tumor types, olaparib may offer a potentially efficacious and less toxic cancer treatment compared with currently available chemotherapy regimens. BRCA1 and BRCA2 defective tumors are intrinsically sensitive to PARP inhibitors, both in animal models [Hay et al., 2009; Rottenberg et al., 2008] and in the clinic [Fong et al., 2009]. The mechanism of action for olaparib results from the trapping of inactive PARP onto the single-strand breaks preventing their repair [Helleday, 2011; Murai et al., 2012]. Persistence of SSBs during DNA replication results in their conversion into the more serious DNA DSBs that would normally be repaired by HR repair. Olaparib has been shown to inhibit selected tumor cell lines in vitro and in xenograft and primary explant models as well as in genetic BRCA knock-out models, either as a stand-alone treatment or in combination with established chemotherapies. Patients will be treated with olaparib 200 mg q12hrs each day of a 21-day cycle in tablet formulation until disease progression, unacceptable toxicity, withdrawal of

consent or death. Tablet formation is preferred over capsule formulation based on recent work demonstrating equivalent efficacy with a reduced pill burden [Mateo et al, 2016].

Pre-clinical experience

The pre-clinical experience is fully described in the current version of the olaparib Investigator's Brochure.

Toxicology and safety pharmacology summary

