6 STUDY INTERVENTION

6.1 STUDY INTERVENTION(S) ADMINISTRATION

Potential trial patients will be pre-identified at participating centers into two cohorts:

- (1) germline or somatic deleterious mutation involving genes critical to the DNA repair through homologous recombination deficiency (HRD), as demonstrated by Next-generation DNA sequencing in a CLIA certified, CAP tested and bioinformatics-validated testing lab prior to enrollment. This could include, but not be limited to one of the following genes: *ARID1A*, *ATM*, *ATR*, *MRE11A*, *NBN*, *PTEN*, *RAD50/51/51B*, *BARD1*, *BLM*, *BRCA1*, *BRCA2*, *BRIP1*, *FANCA/C/D2/E/F/G/L*, *PALB2*, *WRN*, *CHEK2*, *CHEK1*, *BAP1*, *FAM175A*, *SLX4*, *MLL2* or *XRCC* and
- (2) no evidence of HR deficiency.

If a pathogenic mutation in the HR pathway is confirmed and not listed above, the study PI will determine if the patient is eligible based on available clinical or pre-clinical literature.

[figure not shown]
The determination of a deleterious mutation must be supported in the documentation included in the testing, and should include clinical, or pre-clinical literature to support the finding that a

specific mutation results in impaired function of the gene, and thus impaired DNA repair through homologous recombination. Mutations and deletions will be evaluated against the Human Gene Mutation database and other online databases (ClinVar, Breast Cancer Information Core, PubMed) to evaluate the functional relevance, and to make a determination on the likelihood of the mutation resulting in defective homologous recombination-dependent DNA repair. Variants of unknown significance will not be eligible.

The testing may have been done at any time prior to enrollment.

Starting C1D1, olaparib 200mg PO BID will be given concurrently with radiation (25 Gy in 5 fractions). Each cycle is 21 days. Starting on C2D1, Pembrolizumab 200mg IV will be administered on Day 1 every 3 weeks with olaparib 300mg PO BID (12 hours apart). There is no specification regarding the sequence in which the drugs should be given on days when they are administered together. For Cycle 1, patients will be evaluated weekly for 3 weeks with blood tests, clinic visits, and physical exams. Starting Cycle 2, patient will be evaluated every 3 weeks on Day 1 of each cycle.

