6.1.2 DOSING AND ADMINISTRATION

The treatment to be used in this trial is outlined below:

Drug	Dose/Potency	Dose Frequency	Route of Administration	Regimen/Treatment Period	Use
Pembrolizumab	200 mg	Q3W	IV infusion	Day 1 of each 3 week cycle (excluding Cycle 1)	Experimental
Olaparib*	200mg PO BID	daily	PO	Daily during Radiation D1-21	Experimental
Olaparib*	300mg PO BID	daily	PO	Daily Post-Radiation	Experimental
SBRT	25Gy in 5 fractions	daily M-F	N/A	5 days starting Day 1	Experimental

*During radiation portion, Olaparib dose will be 200mg PO BID. When combined with pembrolizumab, Olaparib dose will be 300mg PO BID.

Trial treatment should begin on the day of treatment (Combination SBRT and Olaparib)

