6.1.3 TIMING OF DOSE ADMINISTRATION

6.1.3.1 OLAPARIB

Trial treatment with olaparib should be administered starting on Day 1 of a 21-day cycle. Olaparib tablets will be packed in high-density polyethylene (HDPE) bottles with child-resistant closures. Each dosing container will contain sufficient medication for at least 21 days plus overage. Olaparib will be dispensed to patients on Day 1 and every 21 days thereafter until the patient completes the study, withdraws from the study, or closure of the study. Study treatment is available as a green film-coated tablet containing 100mg or 150mg of olaparib. Patients will be administered olaparib orally twice daily at 200 mg BID concurrently with radiation and 300mg continuously when combined with pembrolizumab. Olaparib tablets should be taken at the same time each day, approximately 12 hours apart with one glass of water. The olaparib tablets should be swallowed whole and not chewed, crushed, dissolved or divided. Olaparib tablets can be

taken with or without food. Trial treatment may be administered up to 7 days before or after the scheduled Day 1 of each cycle (after Cycle 1) due to administrative reasons.

If vomiting occurs shortly after the olaparib tablets are swallowed, the dose should only be replaced if all the intact tablets can be seen and counted. Should any patient enrolled on the study miss a scheduled dose for whatever reason (e.g., because of forgetting to take the tablets or vomiting), the patient will be allowed to take the scheduled dose up to a maximum of 2 hours after that scheduled dose time. If greater than 2 hours after the scheduled dose time, the missed dose is not to be taken and the patient should take their allotted dose at the next scheduled time.

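### The timing of Cycle 2 Day 1 and the olaparib dose around it are specified inconsistently, so the SBRT-to-pembrolizumab interval, the DLT period and the post-SBRT biopsy are not pinned down

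*Combined protocol and SAP*

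**What the plan says.** **Timing of C2D1**

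- Section 6.1: "Each cycle is 21 days. Starting on C2D1, Pembrolizumab 200mg IV will be administered on Day 1 every 3 weeks". With C1D1 as Day 1, C2D1 is nominally Day 22.
- Section 1.3, footnote e: "Cycle 2 Day 1 should start within two weeks of completing combination olaparib and radiation".
- Section 6.1.2 gives SBRT on weekdays, "5 days starting Day 1". Section 4.3 allows the course up to two weeks if weekends or logistics intervene.
- Section 1.3 prints the column for Day 1 of later cycles twice. It is headed ±7 over the dosing rows and ±3 over the biopsy and correlative-blood rows. Section 6.1.3.1 lets treatment be given "up to 7 days before or after the scheduled Day 1 of each cycle (after Cycle 1") for administrative reasons.

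**Olaparib dose**

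- Section 6.1.2 has a 200 mg BID row for the radiation period, labelled Days 1-21, and a 300 mg BID row labelled "Daily Post-Radiation". The footnote to that table, section 6.1 and section 6.1.3.1 tie 300 mg to pembrolizumab.
- Section 2.4: "Patients will be treated with olaparib 200 mg q12hrs each day of a 21-day cycle in tablet formulation until disease progression". It mentions no 300 mg step.
- Appendix 5 requires study treatment to stop at least 3 days before radiation. Section 6.1 gives olaparib concurrently with it.

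**What depends on C2D1**

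- The second biopsy is due within 5 days before C2D1 (section 1.3, footnote d).
- The DLT period runs to Cycle 2 Day 21 (section 6.1.1).

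**The concern.** Section 2.2 rests the trial on giving PD-1 blockade after irradiation combined with PARP inhibition. The interval between the two, and the olaparib taken during it, are therefore part of the experimental treatment. Staff following different passages could start Cycle 2 on different days, or read the olaparib dose differently for the days between the last fraction and C2D1.

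Two other results depend on the same date. The go/no-go decision after six lead-in patients would rest on observation periods of unequal length. The biopsy meant to show immune changes after SBRT plus olaparib could be taken at quite different times relative to radiation.

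**Working it through.** The plan gives no day number for C2D1, so there is no stated figure to reproduce. What follows is calendar arithmetic with C1D1 = Day 1.

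**1. Nominal day and windows.** C2D1 = 1 + 21 = Day 22. ±3 gives Days 19-25; ±7 gives Days 15-29.

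**2. Last fraction (L).** Five weekday fractions from Day 1 end on Day 5 for a Monday start. Tuesday to Friday starts cross one weekend and end on Day 7. The section 4.3 allowance extends L to Day 14.

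**3. Footnote e limit = anchor + 14 days.**

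| Anchor for completion | Limit | Is Day 22 allowed? |
|---|---|---|
| Last fraction, Day 5 | Day 19 | No |
| Last fraction, Day 7 | Day 21 | No |
| Last fraction, Day 14 | Day 28 | Yes |
| End of the Days 1-21 olaparib period | Day 35 | Yes, but 35 − 29 = 6 days past the ±7 window |

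**4. Overlap.** For a Monday start, Days 15-19 satisfy both the Day 19 limit and ±7. Day 19 also satisfies ±3, so one day meets every rule. It does so by starting Cycle 2 after 18 days instead of 21.

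**5. Last fraction to first pembrolizumab = C2D1 − L, under ±7.**

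- L = 5: 15 − 5 = 10 to 29 − 5 = 24 days (nominal 22 − 5 = 17). If footnote e is counted from the last fraction, the upper end falls to 19 − 5 = 14 days.
- L = 14: 15 − 14 = 1 to 29 − 14 = 15 days (nominal 8). Counted the same way, the upper end falls to 28 − 14 = 14 days.

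**6. Second biopsy.** The earliest day is C2D1 − 5. With C2D1 on Day 15 the window is Days 10-14. If L = 14, a biopsy on Days 10-13 precedes the last fraction. This can happen whenever C2D1 − 5 < 14, that is, with C2D1 on Days 15-18.

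**7. DLT period.** C2D21 = C2D1 + 20: nominally Day 42, and Day 35 to Day 49 under ±7.

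**8. Olaparib, passages side by side.**

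| Period | What the passages give |
|---|---|
| Before and during SBRT | 200 mg BID concurrently (6.1, 6.1.2); stop at least 3 days before radiation (Appendix 5) |
| End of SBRT to Day 21 | 200 mg row (Days 1-21) and 300 mg row (post-radiation) both apply on their face (6.1.2) |
| Day 22 to a delayed C2D1 | Not expressly stated |
| From C2D1 | 300 mg BID (6.1, 6.1.2 footnote, 6.1.3.1); 200 mg until progression (2.4) |

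**9. Primary test.** Section 9.2's N = 26, null 0.25 and alternative 0.45 are untouched. Rejecting at 10 or more responses gives exact alpha 0.0909 and power 0.806, in line with the stated 0.1 and 0.8.

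**The case against.** The strongest reply is that the operative text can be read coherently. Counted from Day 21, footnote e is a loose outer limit that contains Day 22 and both windows. The dosing table supports that reading by labelling Days 1-21 as the radiation period, and the footnote is worded as advice. The ±3 heading covers only biopsy and blood rows, while the dosing rows and section 6.1.3.1 agree on ±7. Sections 6.1, 6.1.2 and 6.1.3.1 agree on the order of treatment and on 200 mg with radiation, then 300 mg with pembrolizumab. Section 2.4 is background. The Appendix 5 sentence sits under interruptions for intercurrent events and may have been meant for other radiation. The schema figures are not in the text available here and might show timing.

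Much of this stands, and it rules out three stronger readings that a reader might infer:

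- *The C2D1 rules are mutually incompatible, so the trial does not test one regimen.* Day 19 and Day 35 are two readings of one undefined phrase, and the rules overlap. The sequence is consistent across the operative sections. Nothing in the documents shows that a shift within ±7 days changes the response rate.
- *The interval may reach 30 days and the DLT period Day 55.* Both need C2D1 on Day 35, which breaches the ±7 dosing window.
- *Cycle 1 olaparib could differ by 38%.* The figure compares 400 × 21 = 8,400 mg with 400 × 5 + 600 × 16 = 11,600 mg. The larger total overrides the explicit Days 1-21 label, the table's own footnote and sections 6.1 and 6.1.3.1.

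The reply does not supply the missing anchor in footnote e. Nor does it remove the two headings on one column, the overlapping dose rows, the section 2.4 statement or the unqualified Appendix 5 sentence.

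**Conclusion.** The concern holds as an inconsistency of specification. Footnote e has no defined end point, and its limit ranges from Day 19 to Day 35 with the reading. Counted from an on-schedule last fraction, it excludes the Day 22 that a 21-day cycle requires.

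Within the ±7 dosing window, the interval from radiation to pembrolizumab is 10 to 24 days for SBRT ending on Day 5, and as short as 1 day for SBRT ending on Day 14. In the latter case the biopsy labelled as after SBRT and olaparib could precede the last fraction. The DLT period can differ by 14 days between patients (Day 35 to Day 49). The olaparib statements conflict in three places: the two rows of section 6.1.2, section 2.4 against section 6.1, and Appendix 5 against section 6.1. A fourth period, Day 22 to a delayed C2D1, is not covered.

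These figures assume C1D1 is the first SBRT day, weekday fractions, and ±7 as the governing dosing window. No view is taken on which dose or interval is right.

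**What to change.** Reconcile sections 1.3 (both column headings and footnote e), 2.4, 4.3, 6.1, 6.1.2 and 6.1.3.1 with the radiation sentence in Appendix 5:

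- Tie C2D1 to one named anchor event, with one window.
- Express the olaparib rows by cycle day, and make the text cover the whole period from the last fraction to C2D1, including a delayed C2D1.
- Define the second biopsy so that it falls after the last fraction.
- State whether the Appendix 5 instruction applies to protocol SBRT.

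The sponsor must choose the dose and the interval; none is proposed here. The interval from last fraction to first pembrolizumab can be derived and reported from administration records already kept under section 6.3. The cost is a protocol wording amendment, with no added patients or visits.
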